8.1.1.3 Patient Health Questionnaire-9 (PHQ-9)

The PHQ-9 is a 9-item PRO used to assess severity of depression over the last 2 weeks. It was developed using each of the 9 DSM-IV criteria. On the basis of these criteria, the diagnosis of depressive disorders is made (Kroenke et al. 2001; see

[Appendix 11](#)). Responses are rated based on frequency of symptoms on a 4-point Likert scale, ranging from 0 (not at all) to 3 (nearly every day). Responses are reported using a recall of the last 2 weeks. A total PHQ-9 total score ranging from 0 to 27 can be calculated by summing the nine items, of which a higher score corresponds to more severe depression. Scores of 5, 10, 15, and 20 represent cutpoints for mild, moderate, moderately severe, and severe depression, respectively. It takes approximately 90 seconds to 3 minutes to complete. The PHQ-9 will be administered at baseline, Week 6, and Week 12.

8.1.1.4 Life Events Checklist for DSM-5 (LEC-5)

The LEC-5 standard version is a 17-item PRO designed to screen for potentially traumatic events in an individual's lifetime (Gray et al. 2004; Weathers et al. 2013b; see [Appendix 11](#)). The LEC-5 is intended to gather information about the potentially traumatic experiences a person has experienced. It assesses exposure to 16 events known to potentially result in PTSD or distress and one additional item assessing any other extraordinarily stressful event not captured in the first 16 items. Responses are reported on a 6-point nominal scale of which one or more responses can be made based on whether the event: happened to the individual personally; they witnessed it happen to someone else; they learned about it happening to a close family member or close friend; they were exposed to it as part of their job (e.g., first responders); they are not sure if it fits; it does not apply. There is no formal scoring protocol or interpretation per se, other than identifying whether a person has experienced one or more of the events listed.

The purpose of the LEC-5 generally and in this study is to inform other measures (e.g., CAPS-5) to establish exposure to a PTSD Criterion A traumatic event. It takes approximately 4–8 minutes to complete. The LEC-5 must be completed at the screening visit.

8.1.1.5 PTSD Checklist for DSM-5 (PCL-5)

The PCL-5 is a 20-item PRO used to assess the 20 DSM-5 symptoms of PTSD (Weathers et al. 2013c; Blevins et al. 2015; see [Appendix 11](#)). Responses are reported on a 5-point Likert scale, ranging from 0 (not at all) to 4 (extremely). A recall period of one month has been validated. However, the PCL-5 manual acknowledges a recall period of less than one month may make more sense in some cases, but to be aware that the psychometric properties may differ to those published using the one-month recall (National Center for PTSD 2013). In this study, the one-month recall will be used at screening for diagnostic purposes and a one week recall version will be used thereafter for efficacy. This is to allow for more frequent PCL-5 administrations without overlapping recalls. A total severity score, ranging from 0 to 80, can be calculated by summing all items, of which a higher score corresponds to more severe symptoms. The PCL-5 can be used to determine a provisional diagnosis in two ways; either using a cutpoint score of 31 to 33, or alternatively, by treating each item rated as 2 (moderately) or higher as a symptom endorsed and then following the DSM-5 diagnostic rule, which

requires at least: 1 Criterion B item (Questions 1–5), 1 Criterion C item (Questions 6–7), 2 Criterion D items (Questions 8–14), and 2 Criterion E items (Questions 15–20). If a patient meets a provisional diagnosis using either of the methods above, then he or she needs further assessment (e.g., CAPS-5 or SCID-5) to confirm a diagnosis of PTSD. It takes approximately 5–10 minutes to complete. The PCL-5 will be administered at screening, baseline, Week 2, Week 6, and Week 12.

8.1.1.6 Structured-Clinical Interview for DSM-5 (SCID-5)

The SCID-5 is a structured diagnostic instrument for assessing DSM-5 disorders (First 2014; [Appendix 11](#)). The instrument is designed to be administered by a clinician or trained mental health professional. The SCID-5 is organized into diagnostic modules corresponding to categories of diagnoses. Most sections begin with an entry question that would allow the interviewer to skip the associated questions if not met. For all diagnoses, symptoms are coded as present, subthreshold, or absent. The SCID-5 will be used only at screening for the diagnosis of PTSD.

8.1.1.7 Beck Anxiety Inventory (BAI)

The BAI is a 21-item PRO used to assess severity of anxiety in psychiatric populations (Beck et al. 1988; see [Appendix 11](#)). BAI is a self-reported measure of clinical anxiety. BAI was designed to specifically assess the physiological and cognitive symptoms of anxiety and is independent of depression. Responses are reported using a recall of 1 week on the basis of how much an individual has been bothered by each symptom and then recorded using a 4-point Likert scale, ranging from 0 (not at all) to 3 (severely—it bothered me a lot). A total score, ranging from 0 to 63, can be calculated by summing the 21 items, for which a higher score corresponds to more severe anxiety. Scores of 0 to 21, 22 to 35, and 36 and above represent cutpoints for low, moderate, and concerning levels of anxiety. It takes approximately 2–4 minutes to complete. The BAI will be administered at baseline, Week 6, and Week 12.

8.1.1.8 Pittsburgh Sleep Quality Index (PSQI)

The PSQI is a 19-item PRO used to assess sleep quality over the past month (Buysse et al. 1989; see [Appendix 11](#)). It contains 7 domains, consisting of subjective sleep quality (1 item), sleep latency (2 items), sleep duration (1 item), habitual sleep efficiency (3 items), sleep disturbances (9 items), use of sleep medication (1 item), and daytime dysfunction (2 items). It is rated by entering numeric values or on a 4-point Likert scale with a range of response options from 0 (corresponding to better outcomes) to 3 (corresponding to worse outcomes). Responses are reported using a recall of the past month. The PSQI can be scored as a total score ranging from 0 to 21 by summing all items or by domain (mentioned above), for which higher scores correspond to worse sleep quality. A global score of 5 represents poor sleep quality. It takes approximately 5–10 minutes to complete. The PSQI will be administered at baseline, Week 6, and Week 12.

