
 To investigate the plasma pharmacokinetics of balovaptan 	
 Concentration per timepoint for balovaptan ^a PK parameters as appropriate

Table 2 Objectives and Corresponding Endpoints (cont.)

Exploratory Objectives	
Exploratory Biomarker Objective	Corresponding Endpoints

 To identify and/or investigate biomarkers that are predictive of response to balovaptan (i.e., predictive biomarkers) or are early signs of efficacy 	
 Relationship between biomarkers (e.g., EEG, genomics, digital biomarkers, computerized cognitive battery) and efficacy, safety, PK, or other biomarker endpoints (see Section 8.7)
Exploratory Efficacy Objectives	Corresponding Endpoints

 To investigate the efficacy of balovaptan compared with placebo 	
 Change from baseline at Week 12 on the CAPS-5 symptom cluster scores Proportion of participants with no symptoms, very mild, mild, moderate, severe, very severe in the PGI-S at each scheduled visit Proportion of participants with no change, improvement or worsening in the CGI-C and PGI-C at Weeks 6 and 12 Change from baseline at Week 6 on the CAPS-5 total symptom severity score

 To investigate the efficacy of balovaptan compared with placebo in PTSD symptoms, anxiety, sleep, functioning, and cognition 	
 Change from baseline at Weeks 6 and 12 on the following: 
 PCL-5 total score BAI total score PSQI total and domain scores CPFQ total score and domain scores SDS global score Computerized cognitive battery

BAI=Beck Anxiety Inventory; CAPS-5=Clinician-Administered PTSD Scale for DSM-5; CGI-C=Clinician-Global Impression of Change; CGI-S=Clinician-Global Impression of Severity; CPFQ=Cognitive and Physical Functioning Questionnaire; C-SSRS=Columbia-Suicide Severity Rating Scale; DSM-5=Diagnostic and Statistical Manual of Mental Disorders, Version 5; EEG=electroencephalogram; M2=Metabolite 2; M3=Metabolite 3; PCL-5=PTSD Checklist for DSM 5; PGI-C=Patient-Global Impression of Change; PGI-S=Patient-Global Impression of Severity; PHQ-9=Patient Health Questionnaire-9; PK=pharmacokinetic; PSQI=Pittsburgh Sleep Quality Index; PTSD=Post-traumatic stress disorder; SDS=Sheehan Disability Scale.

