Appendix 11: Clinical Outcome Assessment Instruments

A11–9 PITTSBURGH-SLEEP QUALITY INDEX (PSQI)

(Sample; Not to Be Used to Enter Subject Data)

Pittsburgh Sleep Quality Index (PSQI)

Instructions: The following questions relate to your usual sleep habits during the past month only. Your answers should indicate the most accurate reply for the majority of days and nights in the past month. **Please answer all questions.**

1. During the past month, what time have you usually gone to bed at night? _____
2. During the past month, how long (in minutes) has it usually taken you to fall asleep each night? _____
3. During the past month, what time have you usually gotten up in the morning? _____
4. During the past month, how many hours of actual sleep did you get at night? (This may be different than the number of hours you spent in bed.) _____

5. During the past month , how often have you had trouble sleeping because you...	Not during the past month	Less than once a week	Once or twice a week	Three or more times a week
a. Cannot get to sleep within 30 minutes				
b. Wake up in the middle of the night or early morning				
c. Have to get up to use the bathroom				
d. Cannot breathe comfortably				
e. Cough or snore loudly				
f. Feel too cold				
g. Feel too hot				
h. Have bad dreams				
i. Have pain				
j. Other reason(s), please describe:				
6. During the past month, how often have you taken medicine to help you sleep (prescribed or "over the counter")?				
7. During the past month, how often have you had trouble staying awake while driving, eating meals, or engaging in social activity?				
	No problem at all	Only a very slight problem	Somewhat of a problem	A very big problem
8. During the past month, how much of a problem has it been for you to keep up enough enthusiasm to get things done?				
	Very good	Fairly good	Fairly bad	Very bad
9. During the past month, how would you rate your sleep quality overall?				

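### Section 8.1.1.8 derives the 0–21 PSQI total by adding up every item, but that rule cannot give that range; only seven domain scores of 0–3 can

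*Combined protocol and SAP*

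**What the plan says.** Section 8.1.1.8 introduces the instrument: "The PSQI is a 19-item PRO used to assess sleep quality over the past month". It names seven domains with 1, 2, 1, 3, 9, 1 and 2 items. On response format it says "It is rated by entering numeric values or on a 4-point Likert scale with a range of response options from 0" (better) to 3 (worse). The scoring sentence is: "The PSQI can be scored as a total score ranging from 0 to 21 by summing all items or by domain". Higher scores are said to mean worse sleep, and a global score of 5 is given as marking poor sleep.

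The sample form in Appendix 11, A11-9, shows what is entered. Item 1 asks "what time have you usually gone to bed at night", and item 2 asks "During the past month, how long (in minutes) has it usually taken you to fall asleep each night". Item 3 asks for the time of getting up and item 4 for hours of actual sleep.

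Section 3, Table 2, lists "PSQI total and domain scores" among the exploratory efficacy endpoints, as change from baseline at Weeks 6 and 12. Section 9.4.4 says exploratory endpoints will be summarised descriptively by arm.

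**The concern.** The scoring sentence gives a rule and a range that do not belong together. Clock times, minutes and hours cannot be added to 0–3 codes to give a bounded score, and the four-category items by themselves overshoot 21. The alternative of scoring by domain is named without a method, although domain scores are part of the listed endpoint.

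At stake is whether the reported PSQI change scores follow a rule that a reader can reconstruct. Followed literally, the rule would give a total dominated by raw minutes and clock times. If the instrument's own algorithm is used instead, the analysis will not match the protocol text.

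**Working it through.** **Inputs**

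- Items per domain (Section 8.1.1.8): 1 + 2 + 1 + 3 + 9 + 1 + 2 = 19, in 7 domains.
- Response codes (Section 8.1.1.8): numeric entry, or 0 to 3.
- Form (A11-9), self-rated part before the bed-partner question: four numeric entries (items 1–4) and 14 four-category items (5a–5j, 6, 7, 8 and 9), so 4 + 14 = 18 distinct items. The difference from 19 is explained if hours of sleep counts in both the duration and efficiency domains. That is an inference, and nothing below depends on it.
- Stated range: 0 to 21.

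**Step 1. Try to reproduce 21 under the written rule.**

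| Reading of the rule | Arithmetic | Maximum |
|---|---|---|
| Add the four-category items only | 14 × 3 | 42 |
| Add everything, with numeric entries as written | no upper limit on minutes | unbounded |

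Neither gives 21. The first is 42/21 = 2.0 times the stated maximum. A participant answering 2 on each of the 14 items would score 14 × 2 = 28, already out of range. For the second, take illustrative entries of bedtime 23, 30 minutes, up at 7 and 6 hours: 23 + 30 + 7 + 6 = 66 before any four-category item is counted.

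**Step 2. Try adding items within domains.** Sleep disturbances has nine items: 9 × 3 = 27. One domain would exceed the maximum given for the whole scale.

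**Step 3. Find the rule that does fit.** Seven domain scores, each 0–3: 7 × 3 = 21, with minimum 0. This matches the stated range. The 0–3 range per domain is inferred from 21/7 = 3 and from the 0–3 response codes; the protocol does not state it.

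**Step 4. Check direction.** Higher is said to be worse. In a literal sum, more hours of sleep (item 4) would raise the score, and clock times have no better-to-worse order. Numeric entries must therefore be converted first, and no section says how.

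**Step 5. Check whether item sums work for the neighbouring scales.** They do:

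- PHQ-9: 9 × 3 = 27, stated maximum 27.
- PCL-5: 20 × 4 = 80, stated maximum 80.
- BAI: 21 × 3 = 63, stated maximum 63.
- CPFQ: 7 × 1 = 7 to 7 × 6 = 42, stated range 7 to 42.

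Of these summed scales, the PSQI is the only one with numeric entries and the only one where the rule and range disagree.

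**Step 6. Size if the text were followed literally.** Section 9.2 plans 15 participants per arm. With 15 values in the mean, a 30-minute change in one participant's time to fall asleep would move the arm mean by 30/15 = 2 points, on a scale said to span 21. The 30 minutes is an illustration, not a figure from the protocol.

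**The case against.** The best defence is that Section 8.1.1.8 describes an existing questionnaire and is not a programming specification. It cites the instrument's source publication, which is listed in Section 10, and Section 8.10.1 requires the official version of each instrument. The stated range is the right one for seven domain scores. A programmer who tried to add a bedtime to a 0–3 code would see the contradiction at once. The item responses are collected either way, so a correction before analysis loses nothing.

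Most of this stands, and it limits the consequence. It does not remove the error. No other section corrects the sentence. A11-9 reproduces the form without a scoring key, whereas A11-1 reproduces scoring instructions for the CAPS-5. Section 9.4.4 gives only the summary statistics to be reported.

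The defence also rules out several stronger inferences that a reader might draw:

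- *The reported endpoint will be wrong.* The documents do not show that the sentence will be programmed as written.
- *The protocol is the only scoring specification.* It cites an outside source, which is not available here and cannot be assumed to leave scoring open.
- *The item sum can reach 19 × 3 = 57, or 2.7 times the range.* This treats all 19 items as scored 0–3. The form shows four numeric entries and 14 four-category items, so the supportable figure is 42, or 2.0 times.
- *Losing the cut of 5 damages an analysis.* Table 2 lists no responder or categorical PSQI endpoint, so the cut feeds no listed analysis.

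**Conclusion.** The point holds as a minor correction. The fault lies in the instruction to add items, and in the undefined domain scoring; the 0–21 range itself is coherent. The inconsistency follows from the protocol's own item list and form and needs no outside source. The replacement rule rests on one assumption: that each domain is scored 0–3.

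The reach is narrow. No formal hypotheses are tested (Section 9.1), and the primary endpoint (CAPS-5) and secondary efficacy endpoints (CGI-S and PHQ-9) do not use the PSQI. Nor do the safety endpoints, eligibility or the sample size. The harm is conditional on literal programming. If the cited source is used instead, what remains is a protocol sentence that contradicts the method applied.

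**What to change.** In Section 8.1.1.8, replace the part of the scoring sentence that explains how the total and domain scores are formed with: *by summing the seven domain scores, each derived as 0–3 with the instrument's published scoring algorithm; domain scores are reported on the same 0–3 basis.* Cite or attach that algorithm, and make sure that it covers the conversion of the clock times, minutes and hours and the reduction of multi-item domains to one score. The sponsor should confirm the 0–3 range per domain against the source when making the edit.

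The cost is one sentence and a reference. The form, the visit schedule and the data collected do not change. Any PSQI derivation already programmed should be checked against the corrected text before analysis.

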8.1.1.9 Sheehan Disability Scale (SDS)

The SDS is a 5-item PRO used to assess health-related quality of life and social functioning (Sheehan 1983, Sheehan and Sheehan 2008; see [Appendix 11](#)). It consists of 3 core items that are related to disruption at work, social life, and family life, as well as 2 optional items stating the number of days lost or underproductive due to symptoms. Using a recall period of the past week, items are rated on a 10-point numerical rating scale, ranging from 0 (unimpaired) to 10 (highly impaired). The measure can be scored either by item as a percentage or as a global score from 0 to 30, for which higher scores correspond to greater impairment. There are no referenced cutoff scores for this measure. It takes approximately 1–2 minutes to complete. The SDS will be administered at baseline, Week 6 and Week 12.

8.1.1.10 Cognitive and Physical Functioning Questionnaire (CPFQ)

CPFQ is a 7-item PRO used to assess physical and psychological functioning in mood and anxiety disorders (Fava et al. 2009; see [Appendix 11](#)). The participant is asked to report how affected he or she has been over the past month by seven of the most common complaints of depressed individuals. Responses are made using a 6-point Likert scale from 1 (greater than normal) to 6 (totally absent). Scoring can be calculated as a total score, ranging from 7 to 42 or by domain (cognitive, 4 items; physical, 3 items) by summing items and a higher score corresponds to poorer functioning. It takes approximately 60–90 seconds to complete. The CPFQ will be administered at baseline, Week 6, and Week 12.

8.1.1.11 Patient-Global Impression of Severity (PGI-S) and Change (PGI-C)

The PGI-S and PGI-C are single items rated by the participant that is used to assess the overall severity over the past 7 days or change of PTSD symptoms relative to baseline (see [Appendix 11](#)). Each item is rated on a 7-point scale, ranging from 1 (no symptoms/very much improved) to 7 (very severe/very much worse) for PGI-S and PGI-C, respectively. The assessments will each take approximately 30 seconds to complete. The PGI-S will be collected at baseline, Week 6, and Week 12. The PGI-C will be collected at Week 6 and Week 12.

8.1.1.12 Computerized Cognitive Battery

A computerized cognitive battery will be administered and completed by participants to assess domains such as psychomotor functioning (e.g., simple and choice-reaction time tasks), non-verbal receptive communication (e.g., facial-emotion recognition task), verbal memory, and executive function (including set-shifting and/or reversal learning). The data will be used mainly to derive cognitive biomarkers (see [Section 8.7](#)) and may also be used for exploratory efficacy endpoints. The assessments will take approximately 30 minutes to complete and will be administered at the pre-randomization visit, Week 2, Week 6, and Week 12.

8.2 SAFETY ASSESSMENTS

8.2.1 Physical Examinations

A complete physical examination will include, at a minimum, assessments of the cardiovascular, dermatologic, musculoskeletal, respiratory, gastrointestinal, and neurologic systems. Any abnormality identified at baseline should be recorded on the General Medical History and Baseline Conditions eCRF.

A brief *or limited* physical examination should be symptom-directed and will include, at a minimum, assessments of the skin, lungs, *and the* cardiovascular and neurologic systems.

Investigators should pay special attention to clinical signs related to previous serious illnesses. Changes from baseline abnormalities should be recorded in participant notes. New or worsened clinically significant abnormalities beyond what is expected in the clinical situation should be recorded as adverse events on the Adverse Event eCRF.

8.2.2 Vital Signs

Temperature (tympanic), pulse rate, respiratory rate, and blood pressure will be assessed.

Blood pressure and pulse measurements will be assessed while the participant is in a seated position with a completely automated device. Manual techniques will be used only if an automated device is not available.

Blood pressure and pulse measurements should be preceded by at least 5 minutes of rest for the participant in a quiet setting without distractions (e.g., television, cell phones).

Vital signs (to be taken before any blood collection) will consist of one pulse and three blood pressure measurements (three consecutive blood pressure readings will be recorded at intervals of at least 1 minute). The average of the three blood pressure readings will be recorded on the eCRF.

Abnormalities observed at baseline should be recorded on the General Medical History and Baseline Conditions eCRF. At subsequent visits, new or worsened clinically significant abnormalities should be recorded as adverse events on the Adverse Event eCRF.

8.2.3 Neurological Examination

Neurologic examinations of the upper and lower limbs will be completed as per the schedule of activities in Section 1.3 (see [Table 1](#)) and conducted as per the instructions provided in [Appendix 7](#).

8.2.4 Electrocardiograms

Single 12-lead ECGs will be obtained as outlined in the schedule of activities (see Section 1.3) using an ECG machine that automatically calculates the heart rate and measures PR interval, QRS interval, QT interval, and QTcF. Refer to [Appendix 6](#) for prolonged QTc management criteria and any additional QTc readings that may be necessary.

For the baseline ECG at which triplicate ECGs are required, three individual ECG tracings should be obtained as closely as possible in succession, approximately 1–2 minutes apart.

All ECG recordings must be performed through use of a standard high-quality, high-fidelity digital electrocardiograph machine. Lead placement should be as consistent as possible. ECG recordings must be performed after the participant has been resting in a supine position for at least 5 minutes. All ECGs are to be obtained prior to other procedures scheduled at that same time (e.g., vital sign measurements, blood draws) and should not be obtained within 3 hours after any meal. Circumstances that may induce changes in heart rate, including environmental distractions (e.g., television, radio, conversation) should be avoided during the pre-ECG resting period and during ECG recording.

For safety monitoring purposes, the investigator must review, sign, and date all ECG reports. Paper copies of ECG tracings will be kept as part of the participant's permanent study file at the site. Digital recordings will be stored at the site as part of the medical record and the central ECG laboratory. The following parameters will be provided as non-eCRF data: heart rate, RR interval, QRS interval, PR duration (beginning of P wave to first part of QRS complex), uncorrected QT interval, and QTcF based on machine readings of the individual ECG tracings. Any concerning morphologic waveform changes or other ECG abnormalities that lead to change in management or increased monitoring must be documented on the eCRF as an adverse event.

If at a particular postdose timepoint the mean QTcF is > 500 ms and/or > 60 ms longer than the baseline value, another ECG must be recorded, ideally within the next 30 minutes, and ECG monitoring should continue until QTcF has stabilized on two successive ECGs. The Medical Monitor should be notified. Standard-of-care treatment may be instituted at the investigator's discretion. If a PK sample is not scheduled for that timepoint, one should be obtained. A decision on study drug discontinuation should be made, as described in [Appendix 6](#) (see Section [A6–2.7](#)). The investigator should also evaluate the participant for potential concurrent risk factors (e.g., electrolyte abnormalities, concomitant medications known to prolong the QT interval, severe bradycardia).

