7.1.2 QTc Stopping Criteria

There is no preclinical or clinical evidence that balovaptan administration may be associated with an increase in the corrected QT interval (QTc).

Nevertheless, treatment should be discontinued in case of the following:

- Sustained (at least two ECG measurements >30 minutes apart) QTcF that is >500 ms and/or >60 ms longer than the baseline value

Treatment with balovaptan should be discontinued in participants who develop changes in QT interval, as described in [Appendix 6](#). ECG assessment should be conducted as outlined in Section [8.2.4](#).

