Appendix 6: Safety Plan: Management of Identified and Potential Risks

In the event of reports matching the related adverse events of special interest definition (see Section 8.3.7), participants should be evaluated for use of any concomitant medication as well as occurrence of any recent accidents or physical exercise. In the event that CPK values exceed $10\times$ ULN, confirmatory samples should be obtained within 3–5 days, depending on the actual CPK value and circumstances, for example, whether or not a possible alternative explanation like an accident or sports is present. Serum creatinine and serum potassium levels should be measured at the same time. An ECG recording may provide information about QRS complex changes and arrhythmias potentially related to changes in potassium.

Hydration status should be assessed and intake of fluids is advised. The need for hospitalization and intravenous administration of fluids, respectively, should be considered, depending on the CPK increase and a participant's hydration status. The investigator may decide to temporarily withdraw treatment if no alternative explanation exists and CPK values do not show a trend for normalization according to the half-life of CPK in plasma. Treatment may be re-started once CPK values have shown a clear trend toward normalization and if CPK increases were not associated with relevant kidney dysfunction. CPK levels should be monitored until they are below $2\times$ ULN or in the range of screening and baseline values.

CPK laboratory abnormality as per Section 8.3.7 must be reported as an adverse event of special interest.

CPK values will be assessed at baseline, at Week 6 and Week 12 (see the schedule of activities in Section 1.3 [see Table 1]) as well as at the post-treatment follow-up visit.

A6–2.7 MANAGEMENT OF CARDIAC ADVERSE EVENTS

Increases in the Corrected QT Interval (QTc) Interval

There is no preclinical or clinical evidence that balovaptan administration may be associated with an increase in the QTc interval. Nevertheless, treatment should be discontinued in case of the following:

- Sustained (at least two ECG measurements >30 minutes apart) QT interval corrected through use of Fridericia's formula (QTcF) that is >500 ms and >60 ms longer than the baseline value. In this instance, serum electrolytes, in particular, potassium, and magnesium, as well as use of any concomitant medications should be analyzed as a potential cause of the increase in the QTc interval.

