Management of participants with sustained QTc prolongation should include close monitoring, with ECGs repeated until two successive ECGs show resolution of the findings, correction of any electrolyte abnormalities, and possible discontinuation of other concomitant medications that are known to prolong the QTc interval. Consultation with a

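### The repeat-ECG timing preferred in Section 8.2.4 cannot test the QTc stopping criterion, and no passage requires an ECG that would, so a stable but still prolonged QTcF may go unevaluated within the episode

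*Combined protocol and SAP*

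**What the plan says.** Three places in the combined protocol and SAP deal with a prolonged QTcF during treatment.

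- **Section 8.2.4 (Electrocardiograms)** starts the follow-up when "the mean QTcF is > 500 ms and/or > 60 ms longer than the baseline value". In that case "another ECG must be recorded, ideally within the next 30 minutes, and ECG monitoring should continue until QTcF has stabilized on two successive ECGs". The repeat is mandatory and its timing is a preference. The section does not define what counts as stabilized and sets no interval for ECGs after the first repeat. It also has the Medical Monitor notified, asks for a PK sample if none is scheduled, and sends the decision on study drug to Section A6-2.7.
- **Section 7.1.2 (QTc Stopping Criteria)** has treatment discontinued for "Sustained (at least two ECG measurements >30 minutes apart) QTcF that is >500 ms and/or >60 ms longer than the baseline value". Section 7.1 lists the Section 7.1.2 events among those for which permanent discontinuation is mandatory. For how ECGs are to be done, Section 7.1.2 refers back to Section 8.2.4.
- **Appendix 6, Section A6-2.7** uses the same interval: "Sustained (at least two ECG measurements >30 minutes apart) QT interval corrected through use of" Fridericia's formula "that is >500 ms and >60 ms longer than the baseline value". For participants whose prolongation is already sustained, it asks for close monitoring "with ECGs repeated until two successive ECGs show resolution of the findings".

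Table 1 schedules on-treatment 12-lead ECGs at Week 2 (Day 14) and Week 12 (Day 84) and at no visit in between.

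**The concern.** Section 8.2.4 produces the follow-up ECGs, and Sections 7.1.2 and A6-2.7 use them. The preferred interval in the first is 30 minutes or less, while the interval required by the others is more than 30 minutes. A site that follows the stated preference therefore obtains a pair of ECGs that can neither satisfy nor exclude the stopping criterion. The references are circular as well: Section 7.1.2 points to 8.2.4 for conduct of the ECGs, 8.2.4 points to A6-2.7 for the decision, and neither target requires the ECG that completes the pair.

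The end of monitoring adds to this. A QTcF that has stopped changing while still prolonged can be read as stabilized, so repeat ECGs may cease before 30 minutes have passed. A6-2.7 uses another end point, resolution, once prolongation is sustained, and the documents do not say how the two relate.

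At stake is whether a mandatory safety stopping rule can be applied consistently across about 12 sites. Different sites could reach different decisions on the same QTcF course only because they timed the repeat differently.

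**Working it through.** The plan gives no figure to reproduce here. The check compares the permitted ECG times with the stopping condition.

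**Inputs.** Index ECG at t = 0. First repeat at t1, preferably 30 min or less (8.2.4). Any later ECG at t2, with no interval stated (8.2.4). Stopping condition: two prolonged ECGs with a gap above 30 min (7.1.2, A6-2.7). ECG days 14 and 84 and visit windows of ±3 days (Table 1).

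**Step 1: index and preferred repeat only.** The gap is t1 − 0 = t1. If t1 ≤ 30, the gap is ≤ 30 and the condition of > 30 fails for every such t1.

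**Step 2: what the wording of 8.2.4 allows.**

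| Reading of 8.2.4 | Largest gap | Can the criterion be tested? |
|---|---|---|
| Index and first repeat are the two successive ECGs, t1 ≤ 30 | t1 ≤ 30 min | No |
| Two ECGs after the index are needed, t1 ≤ 30 and t2 not set | t2 | Only if t2 > 30 min |
| First repeat later than 30 min, which the preference allows | t1 > 30 min | Yes |

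Under the second reading, ECGs at 0, 15 and 30 min have a largest gap of 30, which is not above 30. ECGs at 0, 30 and 31 min have a largest gap of 31, which is.

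**Step 3: an illustration (values assumed, not taken from the documents).** QTcF is 512 ms at 0 min, 511 ms at 15 min and 511 ms at 25 min. Take a baseline below 511 − 60 = 451 ms, so that every value is also more than 60 ms above baseline. If stabilized means no longer changing, the last two ECGs end monitoring under 8.2.4 whether or not the index ECG is counted. The largest gap is 25 − 0 = 25 min, so the sustained condition is not met. Because the values exceed both thresholds, the result does not depend on the separate difference between the threshold wording in 7.1.2 (either or both) and A6-2.7 (both).

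**Step 4: the end points.** In this illustration the A6-2.7 requirement to continue until resolution does not come into force, because it covers prolongation already classed as sustained. It therefore does not supply the missing ECG.

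**Step 5: the next scheduled ECG.** After a Week 2 reading: 84 − 14 = 70 days on nominal dates. With the visit windows, the range is (84 − 3) − (14 + 3) = 64 days to (84 + 3) − (14 − 3) = 76 days. Week 12 is also the end of the blinded treatment period.

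**The case against.** A reader might infer that Section 8.2.4 orders the repeat within 30 minutes, so that a participant with persistent prolongation, handled exactly as written, never meets the stopping rule and simply goes home on study drug. The documents do not support that reading, for four reasons.

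- The 30-minute timing is an ideal. A later repeat complies with 8.2.4 and can satisfy the criterion at once.
- Section 8.2.4 does not end with the repeat ECG. The Medical Monitor is notified, risk factors are evaluated, and the decision on study drug is to be made under A6-2.7. The section also refers to Appendix 6 for additional QTc readings.
- Neither 7.1.2 nor A6-2.7 says that both ECGs must come from one episode, so a later unscheduled or scheduled ECG could complete the pair.
- Section 7.1 requires discontinuation on investigator or Sponsor determination, with no ECG interval attached. Section 8 has urgent safety concerns discussed with the Sponsor immediately, and Table 1 allows unscheduled visits with extra safety assessments.

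A reader might also infer that stabilized and resolution contradict each other outright. They can be read as successive steps, because the resolution end point applies only after prolongation is sustained. And if stabilized was meant as a return to acceptable values, a persistently prolonged QTcF would keep monitoring open and a pair over 30 minutes apart would follow in time. Finally, Section A6-1.4 reports a thorough QT study that found no QTc-prolonging effect at 10 mg or 50 mg once daily, so the expected number of such cases is small.

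All of this limits the point without removing it. The referral to A6-2.7 brings the site to a definition that needs a pair of ECGs that nobody has been told to obtain, and A6-2.7 prescribes no readings for prolongation not yet classed as sustained. The other safeguards rest on discretion, whereas the stopping criterion is written as an objective, mandatory rule.

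**Conclusion.** The point holds as a misalignment between procedure and rule. A repeat ECG at the time preferred in 8.2.4 cannot confirm or rule out the criterion in 7.1.2 and A6-2.7, and no passage requires one that can. A stable but still prolonged QTcF may therefore be unevaluable against the stopping rule within that episode. This is a permitted path, not an inevitable one.

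Its reach is bounded by the safeguards above and by the low expected QT risk. If none of the discretionary steps produces a further ECG, the next scheduled one after Week 2 is nominally 70 days later (64 to 76 days within visit windows). That figure is only the gap between scheduled ECGs; it does not show that no ECG would be done in the meantime.

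The conclusion assumes that stabilized, which is undefined, can be read as unchanged rather than normalized, and that the site follows the preferred timing. It does not depend on which threshold wording applies. The sponsor should correct this; it does not call the trial's safety monitoring as a whole into question.

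**What to change.** Reconcile Sections 8.2.4, 7.1.2 and A6-2.7 so that the ECGs obtained after a prolonged reading allow the sustained criterion to be confirmed or ruled out. Define stabilized in 8.2.4, and state how it relates to resolution in A6-2.7 and at which stage each applies. An early repeat and a later confirmatory ECG are compatible, so reconciling the text need not mean giving up either. The sponsor chooses the interval and the end point; this review takes no view on which is right.

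The cost is a few sentences in an amendment. For an affected participant it is at most a slightly longer visit or one further ECG.
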